### 7.6.1 Second Islet Transplant

Islet transplant recipients with partial islet graft function (see Study Definitions) will be considered for a second islet transplant in the interim between 85 days and 8 months post-initial infusion. Islet transplant recipients with **graft failure** will be considered for a second islet transplant before 85 days post-initial infusion. In addition to meeting the criteria outlined below, approval from the Steering Committee must be obtained in advance. Please refer to the MOP for details on this process, which includes review of the potency testing from the first transplant product and post-transplant clinical data.

In order to be eligible for a **second islet transplant**, the following requirements must be met:

1. Subject received  $\geq 5,000$  IE/kg with the first transplant, but failed to achieve or maintain insulin independence.
2. Subject has been compliant with study monitoring and prescribed immunosuppressive therapy.
3. Subject has no unresolved SAEs.
4. No evidence of progressive renal dysfunction, with blood creatinine rising above 2.0 mg/dL (177  $\mu$ mol/L).
5. No evidence of hypersensitization, allergic responses, or other potentially serious drug reactions to medications required by the protocol.
6. PRA  $\leq 50\%$  by flow cytometry (assessment performed locally) and the alloantibody specificity not cross-reactive with antigen(s) present in the subsequent islet preparation in order to avoid unacceptable antigen(s).
7. Absence of any medical condition that, in the opinion of the investigator, will interfere with a safe and successful second islet transplant.

If graft failure occurs after the second islet transplant, these recipients will be considered **treatment failures** with no islet graft function, and immunosuppression will be withdrawn.

### 7.6.2 Third Islet Transplant

The option of a **third islet transplant** under this protocol will be considered only if all of the following conditions are met:

1. The subject received greater than 4,000 IE/kg with the second transplant, but remains dependent on insulin for longer than one month after the second transplant.
2. There is evidence of **partial graft function**.
3. The CIT PIs, Site PI, and the Steering Committee have determined that there were no relevant protocol deviations at the site.
4. The subject has been compliant with study monitoring and prescribed immunosuppressive therapy.
5. No evidence of a serious and life-threatening infection, AE, or other condition that precludes attempting an intraportal injection or continuation of the post-transplant treatment regimen.
6. No evidence of post-transplant lymphoproliferative disorder (PTLD).
7. No evidence of progressive renal dysfunction, with blood creatinine rising above 2.0 mg/dL (177  $\mu$ mol/L).
8. No evidence of hypersensitization, allergic responses, or other potentially serious drug reactions to medications required by the protocol.
9. No evidence of abnormal liver ultrasound and LFTs within 1.5 times the ULN range.
10. PRA  $\leq$  50% by flow cytometry (assessment performed locally) and the alloantibody specificity not cross-reactive with antigen(s) present in the subsequent islet preparation in order to avoid unacceptable antigen(s)

The third transplant must occur prior to 8 months post-first islet transplant.

### 7.7 Visit Windows

Study visits should take place within the time limits specified on the Schedule of Events (Appendices 1, 2, 3, and 4).

## 8. SAFETY MONITORING

AEs that are classified as serious according to the definition set forth by the health authorities must be reported promptly to NIAID/NIDDK, Clinical Research Organization (CRO)/Data Coordinating Center (DCC), health authorities, PIs, and (IRBs). This section defines the types of AEs and outlines the procedures for appropriately collecting, grading, recording, and reporting them. Information in this section complies with *International Conference on Harmonization (ICH) Guideline E2A: Clinical Safety Data Management: Definitions and Standards for Expedited Reporting* and *ICH E6: Guideline for Good Clinical Practice*, and applies the standards set forth in the most current version of the *CIT-TCAE*. This document, created by the CIT Consortium, modifies the National Cancer Institute (NCI), *Common Terminology Criteria for Adverse Events (CTCAE)* version 3.0 (*June 10, 2003*), to ensure applicability in the setting of Islet Transplantation.

### 8.1 Definitions

#### 8.1.1 Adverse Event

An AE is any occurrence or worsening of an undesirable or unintended sign, symptom (including an abnormal laboratory finding), or disease that is temporally associated with the use of a study-related treatment whether considered related to the treatment or not.

#### 8.1.2 Serious Adverse Event

An SAE is defined, per 21CFR§312.32, as “any AE occurring at any dose that suggests a significant hazard, contraindication, side effect, or precaution”. This includes but is not limited to any of the following events:

1. Death. A death that occurs during the study or that comes to the attention of the investigator during the protocol-defined follow-up after the completion of therapy must be reported whether it is considered to be treatment related or not.
2. A life-threatening event. A life-threatening event is any adverse therapy experience that, in the view of the investigator, places the patient or subject at immediate risk of death from the reaction as it occurred.
3. Inpatient hospitalization or prolongation of existing hospitalization. Please note that hospital admissions for the purpose of conducting protocol-mandated procedures do not need to be reported as SAEs, unless the hospitalization is prolonged due to complications.
4. Persistent or significant disability.
5. Congenital anomaly or birth defect.
6. An event that required intervention to prevent permanent impairment or damage. An important medical event that may not result in death, be life threatening, or require hospitalization may be considered an SAE when, based on appropriate

medical judgment, it may jeopardize the subject and may require medical or surgical intervention to prevent one of the outcomes listed in this definition.

7. Other conditions specified in the protocol.

In addition, events that occur at a higher than expected frequency, as determined by appropriate medical judgment, may be considered SAEs.

Regardless of the relatedness of the AE to study drug, the event must be identified as an SAE if it meets any of the above definitions.

Following the subject's written consent to participate in the study, all SAEs should be collected, including those thought to be associated with clinical trial procedures. Following study completion, any SAE thought to be related to study drug or clinical trial procedures should also be reported to the sponsor.

### 8.1.3 Unexpected Adverse Event

An AE is considered "unexpected" when its nature (specificity) or severity is not consistent with available product information, such as safety information provided in the package insert, the protocol or the investigator's brochure.

## 8.2 Adverse Events

### 8.2.1 Collecting Procedure

AEs that are associated with a protocol mandated procedure, which is not part of the normal standard of care of the participant, and **severe hypoglycemic events** (see study definitions) will be collected beginning immediately after the enrollment consent has been obtained. All other AEs will be collected beginning immediately after randomization. All AEs will continue to be collected until study completion, or for 56 days after the subject prematurely withdraws from the study. AEs will be followed until the time the event is resolved, stabilized, or the subject completes or withdraws from the study, whichever comes first. For transplants that occur as a standard of care procedure at the University of Alberta, adverse events will be collected and submitted by the site investigator until all CIT04 study visits have been completed. If a subject enrolls in a non-CIT islet transplant study, adverse events will no longer be collected in CIT starting at the time of the non-CIT study intervention. All adverse event reporting from that point on will be done through the non-CIT study.

AEs may be discovered through any of these methods:

- Observing the subject.
- Questioning the subject, which should be done in an objective manner.
- Receiving an unsolicited complaint from the subject.
- An abnormal value or result from a clinical or laboratory evaluation (e.g., a radiograph, an ultrasound, or an electrocardiogram) can also indicate an AE. If this is the case, then the evaluation that produced the value or result should be repeated

until the value or result returns to normal or can be explained and the subject's safety is not at risk. If an abnormal value or result is determined by the investigator to be clinically significant, it must be indicated as such on the appropriate laboratory evaluation form(s), and must also be reported as an adverse event on the adverse event form AE.

AEs should be followed to resolution or stabilization, and reported as SAEs if they become serious. This also applies to subjects experiencing AEs that cause interruption or discontinuation of investigational product, or those experiencing AEs that are present at the end of their participation in the study; such subjects should receive post-treatment follow-up as appropriate. If an ongoing AE changes in its severity or in its perceived relationship to study drug, a new AE entry for the event should be completed.

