#### **Potential Risks in Renal Transplantation**

##### *Post-transplant Lymphoproliferative Disorder*

In the combined BMS-sponsored Phase 2 (median exposure 74 to 88 months) and Phase 3 studies (median exposure of approximately 39 months) in de novo renal transplantation, post-transplant lymphoproliferative disorder (PTLD) developed more frequently in patients who received belatacept (14 cases out of 949; 1.5% of subjects) than those who received cyclosporine (3 cases out of 476; 0.6%). Of the PTLD cases reported with belatacept, all but 1 occurred during the first 18 months post transplant. More than half of the PTLD cases in belatacept-treated patients involved the CNS (9 cases out of 14; 65% of belatacept patients). A total of 8 out of 14 patients with PTLD in the belatacept group and 3 out of 3 in the cyclosporine group have died.

The excess risk of PTLD with belatacept was concentrated in EBV negative recipients (approximately 10-fold higher than that observed in EBV positive recipients). While there was also an increased risk in EBV positive subjects with belatacept compared to CsA within the studies, the absolute risk in this population was low. In addition to EBV-negative serostatus, CMV disease, and use of lymphocyte depleting therapy for treatment of AR were also associated with an increased risk of PTLD in the core belatacept studies. Nonetheless, the highest risk of PTLD with belatacept was observed in EBV-negative subjects. Thus, belatacept should not be administered to belatacept naïve patients who are EBV-negative or have unknown EBV serostatus. PTLD should be considered in subjects who develop new neurologic signs or symptoms.

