### **7.5 Follow-up Visits**

Subject will undergo a 24-month follow-up period following their final islet transplant. Please refer to the Schedule of Events (Appendices 1, 2, 3, and 4), for the clinical time points of specific follow-up study procedures.

All subjects will follow the Year One Schedule of Events (Appendix 1) in its entirety. Subjects who receive a subsequent islet transplant will continue onto Appendix 2, Continuation of Appendix 1 Schedule of Events (Subjects with Subsequent CIT Transplants) until they reach their one year visit after the final islet transplant. In addition to following Appendix 2, all

subjects who receive a subsequent transplant should complete the assessments listed on the Subsequent Transplant Schedule of Events (Appendix 3), which provides immediate post-transplant and endpoint day assessments. After the one year post-final transplant visit, subjects will move to Appendix 4, Schedule of Events for 1-Year Additional Follow-up.

Subjects are ineligible for subsequent islet transplantation in the CIT04 protocol as of 8 months following their initial transplant (between visits 16 and 17). After visit 21 (365 days following transplant) has been completed, study subjects may obtain a subsequent islet transplant outside of CIT04. Subjects will be followed for adverse events only until until 24 months after their final CIT islet transplant.

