#### **Reporting of AE Information Following Study Completion**

Collection of safety information following the end of investigational product administration is important in assisting in the identification of possible delayed toxicities or withdrawal effects. In this trial, all SAEs must be collected that occur within 56 days following discontinuation of dosing. In addition, the investigators should report any SAE that may occur after this time period which they believe to be certainly, probably, or possibly related to the investigational product. Finally, all events of death, graft loss, malignancy, PTLD, and serious infections (i.e., otherwise meeting SAE reporting requirements) must be reported for all randomized subjects until the end of the study, irrespective of study drug discontinuation or investigator-deemed causality.

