### 8.3 Serious Adverse Events

#### 8.3.1 Collecting Procedure

SAEs will be collected following the subject's signing of the enrollment consent to participate in the study until 56 days after the subject completes or withdraws from the study. SAEs will be followed until the time the event is resolved, stabilized, or until 56 days after the subject completes or withdraws from the study, whichever comes first.

In addition, SAEs that occur after this time period that are believed to be certainly, probably, or possibly related to the investigational agent will be collected.

For transplants that occur as a standard of care procedure at the University of Alberta, serious adverse events will be collected and submitted by the site investigator until all CIT04 study visits have been completed. If a subject enrolls in a non-CIT islet transplant study, serious adverse events will no longer be collected in CIT starting at the time of the non-CIT study

intervention. All serious adverse event reporting from that point on will be done through the non-CIT study.

The sponsor will request copies of serious adverse events that occur in the non-CIT study from the Principal Investigator for informational purposes.

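### Sections 8.2.1 and 8.3.1 end AE and SAE collection at a non-CIT islet study intervention, while sections 7.5, 8.2.2 and 4.1.2.2 run to two years, so late safety events may be missing from the CIT04 results

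*Protocol*

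**What the plan says.** Section 7.5 allows a further transplant elsewhere once visit 21 (day 365) is complete: "study subjects may obtain a subsequent islet transplant outside of CIT04". The next sentence sets the follow-up: "Subjects will be followed for adverse events only until until 24 months after their final CIT islet transplant". It makes no exception for subjects who enter another study.

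Section 8.2.2, under the heading on AE information following study completion, names a set of events to be kept whatever else happens: "PTLD, and serious infections (i.e., otherwise meeting SAE reporting requirements) must be reported for all randomized subjects until the end of the study". The requirement applies regardless of whether study drug was stopped and of any causality judgement.

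Section 4.1.2.2 places safety endpoints, including infections and neoplasms, at two years after the final islet transplant.

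Section 8.2.1 says otherwise for one group: "If a subject enrolls in a non-CIT islet transplant study, adverse events will no longer be collected in CIT starting at the time". The moment meant is when the other study's intervention begins. Section 8.3.1 repeats this for serious events: "If a subject enrolls in a non-CIT islet transplant study, serious adverse events will no longer be collected in CIT" from that point. Both sections hand later reporting to the other study. Section 8.3.1 adds: "The sponsor will request copies of serious adverse events that occur in the non-CIT study from the Principal Investigator for informational purposes".

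The same two sections treat a standard-of-care transplant at one named site differently. There, AE and SAE collection continues until all CIT04 visits are done.

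**The concern.** A site with a subject who has started a non-CIT islet study cannot follow all of these instructions. Under 7.5 and 8.2.2 it keeps reporting; under 8.2.1 and 8.3.1 it stops. If it stops, an event that 8.2.2 requires for all randomized subjects may never reach the CIT04 database. A statistical analysis plan can decide how to summarise late events, but it cannot recover events that were not collected.

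The trial has 10 subjects, and late harm from the immunosuppression is one of the things it is meant to describe. The two-year safety summaries should not rest on a collection period that differs between subjects without saying so.

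**Working it through.** **The rules side by side, for a subject starting a non-CIT islet study after visit 21**

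| Section | What is collected | Until when |
|---|---|---|
| 7.5 | Adverse events | 24 months after final CIT transplant |
| 8.2.2 | Death, graft loss, malignancy, PTLD, serious infections | End of study, all randomized subjects |
| 4.1.2.2 | Safety endpoints, including infections and neoplasms | Two years after final transplant |
| 8.2.1 | AEs | Non-CIT intervention |
| 8.3.1 | SAEs | Non-CIT intervention |

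**Has the subject left the study?** No. Section 6.1 of CIT04 does not list entry into another islet study as a reason for withdrawal. The CIT08 extension protocol in the same file does list it, in its own section 6.1. So the CIT04 subject is still on study while collection has stopped.

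**Do the safeguards close the gap?**
- The SAE copies are requested for information. Nothing says they enter the CIT04 safety data, and no copies of non-serious AEs are requested.
- Section 8.3.1 also collects later SAEs believed related to the investigational agent. That clause applies after the ordinary collection period (56 days after completion or withdrawal). It also depends on a causality judgement, which 8.2.2 removes for its named events.

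**Length of the gap.** Take 24 months as 730 days, so one month is 730/24 = 30.4 days.
- Earliest opening: visit 21, nominally day 365 after the first transplant (7.5).
- Single transplant: 730 − 365 = 365 days lost at most, which is 365/730 = 50% of follow-up.
- Final CIT transplant near 8 months, the latest allowed (7.5, 7.6.2): 8 × 30.4 = day 243. Follow-up ends at 243 + 730 = day 973. At most 973 − 365 = 608 days are lost, which is 608/973 = 63% of the time from first transplant. Day 365 is then only 365 − 243 = 122 days after that last transplant.

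**Overlap with the PTLD period.** Section 1.5.2 says of the 14 belatacept cases in the renal trials that "all but 1 occurred during the first 18 months post transplant", so 14 − 1 = 13 fell within 18 months. Eighteen months is 18 × 30.4 = day 547. After a single transplant the gap covers 547 − 365 = about 182 days, or about 6 of those 18 months. The protocol does not say how many of the 13 cases fell between months 12 and 18.

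**Expected PTLD.** The cited rate is 14/949 = 1.48%, which agrees with the stated 1.5%. In 10 subjects over all follow-up the expected count is 10 × 0.01475 = 0.15, and P(at least one) = 1 − (1 − 0.01475)^10 = 13.8%. The part falling in the gap is smaller. The cited excess risk was concentrated in EBV-negative recipients, whom this trial excludes.

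**Person-time, as an assumption.** The protocol does not say how many subjects would enter another study. If 1 to 3 of 10 single-transplant subjects left at day 365, the loss would be 1 to 3 of 20 person-years, or 5% to 15%.

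**The case against.** The best defence is that 8.2.1 and 8.3.1 are a specific exception to a general rule. Section 7.5 covers any transplant outside CIT04, including standard of care. The later sections then deal with the research case, where another study has its own reporting, so events are transferred and not simply abandoned. Ending collection at a new study intervention also avoids mixing its harms with those of belatacept. This has force against 7.5, although 7.5 states no exception. It has little against 8.2.2, which covers all randomized subjects to the end of the study. Mixed attribution also arises after a standard-of-care transplant, where collection continues.

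A reader might infer more than the documents support:
- That PTLD will drop out of the results. Section 8.2.2 requires it and the sponsor requests SAE copies, so loss is a risk if 8.2.1 and 8.3.1 are taken to override 8.2.2; it is not certain.
- That counting depends on how the next transplant is funded. The distinction drawn is between a research study and standard of care; funding is not mentioned.
- That the subjects lost are those with failing grafts, so that the loss is selective. This is plausible, but no section says which subjects, if any, would enter another study.
- That one missed case shifts the rate by 10 percentage points. That is true of any event with n = 10 and says nothing about this rule.

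**Conclusion.** The contradiction stands, and its clearest form is 8.2.1 and 8.3.1 against 8.2.2. A site following the first two can omit events that the third says must be reported, in subjects who have not been withdrawn. The existing safeguards do not ensure that those events reach the CIT04 safety results.

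The size is bounded. Only subjects who start a non-CIT islet study intervention after visit 21 are affected, and their number is unknown and could be zero. Each could lose up to 365 of 730 days after a single transplant, or up to about 608 days after a final CIT transplant near 8 months. Both figures are maxima that assume exit at day 365. The expected PTLD count is too small to carry the argument; the point rests on late harms in general and on the conflicting rules. It is worth correcting because the correction is cheap, not because a large bias has been shown.

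**What to change.** Reconcile sections 7.5, 8.2.1, 8.2.2 and 8.3.1.

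1. State in 8.2.1 and 8.3.1 that the events named in 8.2.2 continue to be reported to the end of CIT04 follow-up after a non-CIT intervention.
2. Enter the SAE copies already requested into the CIT04 safety data, flagged as occurring after that intervention, and summarise safety with and without them.
3. For other AEs, amend 7.5 or 8.2.1 so that both give the same end of collection. If follow-up is to be censored at the non-CIT intervention, say so explicitly.

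The cost is a protocol wording change and data entry for a few records. There are two drawbacks. Attribution is mixed after the new intervention, which the flag and the paired summaries handle. Completeness also depends on the other study supplying the copies, since the protocol says only that they will be requested. No dose or treatment rule changes.

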### **8.2.2 Recording Procedure**

Throughout the study, the investigator will record all adverse events on the appropriate AE case report form (CRF) regardless of their severity or relation to study medication or study procedure. The investigator will treat subjects experiencing AEs appropriately and observe them at suitable intervals until their symptoms resolve or their status stabilizes.

#### **Reporting of AE Information Following Study Completion**

Collection of safety information following the end of investigational product administration is important in assisting in the identification of possible delayed toxicities or withdrawal effects. In this trial, all SAEs must be collected that occur within 56 days following discontinuation of dosing. In addition, the investigators should report any SAE that may occur after this time period which they believe to be certainly, probably, or possibly related to the investigational product. Finally, all events of death, graft loss, malignancy, PTLD, and serious infections (i.e., otherwise meeting SAE reporting requirements) must be reported for all randomized subjects until the end of the study, irrespective of study drug discontinuation or investigator-deemed causality.

